3.3.2. Benefit Assessment

The proposed study with GSK2982772 will be conducted in healthy volunteers; no medical benefit will be derived by volunteers' participation. Subjects will indirectly gain through their contribution to the process of developing new therapies in an area of unmet need.

3.3.3. Overall Benefit:Risk Conclusion

The known risks associated with GSK2982772 can be appropriately mitigated by the careful selection of study participants and the proposed safety monitoring procedures. As such, the risk to potential subjects is considered low. Routine safety and tolerability will be evaluated from reported AEs, scheduled physical examinations, vital sign measurements, cardiac rhythm monitoring, 12-lead ECGs, and clinical laboratory test results as well as continued observation by clinical staff.

The study will be conducted in a hospital-based unit or unit with immediate access to hospital facilities for the treatment of medical emergencies. The in-house periods as detailed in the SoA (Section 2) will allow for continuous medical monitoring for all subjects following the first dose in each treatment group. Subjects will only be discharged from the unit 48 hours post-dose if the Investigator deems it safe to do so.

Taking into account the measures taken to minimize risk to subjects participating in this study, the potential risks identified in association with GSK2982772 are justified by the anticipated benefits that may be afforded by the future development of a new therapy in an area of unmet need.

4. OBJECTIVES AND ENDPOINTS

[figure not shown]
Objective	Endpoint
Primary	

 To investigate the safety and tolerability of repeat doses of GSK2982772 in healthy subjects. 	
 Adverse events. Clinical laboratory values (clinical chemistry, haematology and urinalysis). Vital sign measurements (blood pressure, heart rate, respiratory rate and body temperature). Physical examinations. 12-Lead ECG monitoring.
Secondary	

 To characterise the pharmacokinetic (PK) profile of repeat doses of GSK2982772 in healthy subjects. 	
 A 24 hr profile to be collected on Day 1 of Part A and Day 14 of Part B. On Day 1 of Part B, the PK profile will be evaluated following the first dose only. Derived PK parameters for GSK2982772, including area under the plasma drug concentration versus time curve over 24 hr ($AUC_{(0-24)}$) and AUC over each dose interval (i.e. $AUC_{(0-7)}$, $AUC_{(7-14)}$ and $AUC_{(14-24)}$ for TID and $AUC_{(0-12)}$ and $AUC_{(12-24)}$ for BID). Maximum observed plasma drug concentration (C_{max}) following each dose, time to maximum observed plasma drug concentration (T_{max}) following each dose, observed trough plasma drug concentrations (C_0, C_7, C_{14} and C_{24} for TID dosing and C_0, C_{12} and C_{24} for BID dosing).

 To assess the impact of food on the PK of repeat doses of GSK2982772 in healthy subjects at steady state 	
 Derived PK parameters for GSK2982772, including $AUC_{(0-7)}$, $AUC_{(7-14)}$, C_{max}, after 1st dose of day and T_{max} after 1st dose of day.

 To assess potential effect of repeat doses of GSK2982772 on CYP3A4 enzyme activity. 	
 Plasma 4β-hydroxycholesterol to cholesterol ratio pre-treatment and following 14 days of repeat dosing of GSK2982772.
Exploratory	

 To investigate the levels of circulating glucuronide metabolite (M8; GSK3562183) and desmethyl metabolite (M9; GSK2997852) in healthy subjects after repeat dosing of GSK2982772. 	
 Quantify M8 (GSK3562183) and M9 (GSK2997852) in select plasma PK samples at pre-dose and 2 hr following Day 14 of repeat dosing of GSK2982772.

5. STUDY DESIGN

5.1. Overall Design

This is a single-centre, randomized, double-blind (sponsor-unblinded), placebo-controlled study to evaluate the safety, tolerability and pharmacokinetics of GSK2982772, in repeat oral doses in healthy subjects. The study design schematic is depicted in [Figure 1](#).

Figure 1 Study Design

*With Food Effect Treatment

This study is planned to include approximately 48 subjects and consists of 2 parts:

- Part A (Cohort 1) – single ascending dose, randomized, placebo-controlled, 3-way crossover.
- Part B (Cohorts 2, 3 and 4) – repeat dose, randomized, placebo-controlled, sequential-group.

For TID dosing, GSK2982772 or placebo will be administered using a 7hr, 7hr and 10hr dosing interval. For BID dosing, GSK2982772 or placebo will be administered using a 12hr dosing interval.

The impact of food on the PK of GSK2982772 will be investigated during the 14 Day repeat dose phase of the study (Part B) in Cohorts 2 and 3. On Days 1 to 14, subjects will fast for 8hr overnight. Breakfast will be served 2hr after dosing on Days 1 through 8, 10,

12 and 14. A standard breakfast will be served 30 minutes prior to dosing on Day 9, and a high fat breakfast will be served 30 minutes prior to dosing on Day 11.

All of the Cohorts in this study will be double-blind with respect to the subjects, investigator and site staff (with the exception of the site pharmacist). The Sponsor, the GSK study team, will be unblinded throughout.

5.2. Number of Participants

Sufficient number of healthy subjects will be enrolled, such that approximately 12 subjects in each Cohort complete dosing and critical assessments. If subjects prematurely discontinue the study, additional replacement subjects may be randomized in order to guarantee that sufficient subjects are treated with GSK2982772 at any given dose before escalating to the following dose. Subjects that participate in Part A of the study cannot participate in Part B.

5.3. Sentinel Dosing

Sentinel dosing will be employed within each dosing period in Part A of the study. The doses in the single-ascending dose portion of the study (Part A) will be staggered such that for each of the three treatment periods, on Day 1, two of the 12 subjects will be randomized to treatment (one subject will receive GSK2982772 and one subject will receive matched-placebo). Assuming 2 subjects are dosed on Day 1 and assuming adequate safety in the judgment of the Principal Investigator (e.g., vital signs, ECGs, and AEs) through approximately 24 hours after their last dose on Day 1, the remaining subjects may be randomized to dosing in that period. The doses in the repeat dose portion of the study (Part B) will be staggered such that for each treatment period on Day 1, two of the 12 subjects will be randomized to treatment (one subject will receive GSK2982772 and one subject will receive matched-placebo) and dosed for at least 7 days before the rest of the cohort is randomized. If participants prematurely discontinue the study, additional replacement participants may be recruited and assigned to the same treatment sequence, at the discretion of the Sponsor in consultation with the investigator.

5.4. Dose Escalation Decisions

The decision to proceed to the next dose level of GSK2982772 within the study will be made by a Dose Escalation Committee (DEC) consisting of Principal Investigator, or delegate, and other relevant GSK clinical staff (See Section 10.5).

5.5. Participant and Study Completion

A participant is considered to have completed the study if he/she has completed all phases of the study including the last scheduled procedure shown in the SoA (Section 2).

The end of the study is defined as the date of the last visit of the last participant in the study or last scheduled procedure shown in the SoA for the last participant in the trial globally.

5.6. Scientific Rationale for Study Design

In Part A, each cohort will initially evaluate the safety, tolerability and PK of GSK2982772 administered for 1 day as a TID or BID dosing regimen (Cohort 1).

In Part B, the 14-day TID or BID repeat dosing (Cohort 2, 3 and 4) was chosen since it will provide sufficient safety and tolerability data to bridge to longer duration studies with the recently achieved safety margins from the 13-week toxicology study in monkeys. In the previous FTiH study (200975), GSK2982772 was administered up to 120 mg BID for 14 days and was well tolerated with no safety concerns identified. Please see GSK2982772 IB [GlaxoSmithKline Document Number [2014N204126_02](#)].

Cohort 4, 360 mg BID dosing regimen, may only be evaluated if the results of a modified release (MR) formulation study (205017) being conducted in parallel with the current study indicate that a MR formulation is not feasible for GSK2982772. In which case a BID regimen using the current immediate release formulation may be taken forward in to Phase 2a PoC studies. Additionally, Cohort 4 dose may be modified to include the repetition of a previous or lower TID or BID dose based on the results of the safety and tolerability review or if further characterization of the safety profile at a previously tested dose is required.

In the previous FTiH (Study 200975), the impact of a high-fat meal on the absorption of GSK2982772 was investigated following single dose administration of GSK2982772 at a dose of 40 mg. The rate and extent of absorption was similar in the fed state as compared to the fasted state, although there was evidence of a time lag in the absorption in the fed state, probably as a result of delayed gastric emptying. It is likely that higher doses to be used in this study will have a similar food effect to that observed at 40 mg. Therefore, this study plans to evaluate the impact of food during the repeat dose phase in Cohorts 2 and 3 rather than conducting a standalone single dose food effect PK study.

5.7. Dose Justification

An adaptive dose-escalation approach, guided by the observed safety, tolerability and plasma PK exposure will be taken to allow an efficient evaluation of a range of doses above the 120 mg BID dose that was evaluated in the FTiH study.

The initial starting dose planned is 120 mg TID and the maximum daily dose is anticipated to be approximately 720 mg administered as 240 mg TID and 360 mg BID.

For doses of up to 120 mg BID, the pharmacokinetics of GSK2982772 are approximately linear. Please see GSK2982772 IB [GlaxoSmithKline Document Number [2014N204126_02](#)]. After attainment of C_{max} , at approximately 2 hours post-dose, GSK2982772 concentrations decline rapidly until about 12 hours post-dose, with a $t_{1/2}$ of approximately 2 to 3 hours. The majority of the systemic exposure to GSK2982772 is observed within the first 12 hours after administration. Following repeat dosing of GSK2982772, there is no evidence of drug accumulation for either a QD or BID dosing regimen. The major circulating metabolite is an N-glucuronide which accounts for approximately 70% of drug related material in plasma. Since glucuronidation is a high

capacity clearance mechanism it is unlikely that the kinetics of GSK2982772 will become saturable with more frequent dosing nor at the higher doses planned in the current study.

Due to the short half-life of GSK2982772 (~2-3 hr), it is expected that steady-state will be achieved by Day 2 of dosing and that negligible accumulation will be observed. Therefore, the PK safety margins described for Day 1 and for Day 14 of dosing will be similar.

The predicted mean $AUC_{(0-24)}$ for the highest planned doses of 240 mg TID and 360 mg BID ($40.2 \mu\text{g}\cdot\text{h}/\text{mL}$) approximates parity with the mean $AUC_{(0-24)}$ observed at the NOAEL (30 mg/kg/day) in the 13-week monkey toxicology study ($48.4 \mu\text{g}\cdot\text{h}/\text{mL}$). Mean C_{max} values for the 240 mg TID ($3.21 \mu\text{g}/\text{mL}$) and 360 mg BID ($4.31 \mu\text{g}/\text{mL}$) doses are predicted to be $1/4^{\text{th}}$ and $1/3^{\text{rd}}$ respectively, of the C_{max} observed at the NOAEL ($12.3 \mu\text{g}/\text{mL}$). The doses for Cohorts 2 and 3 may be adjusted based on PK/safety data from previous treatment periods. It is planned that the 95th percentile for the predicted $AUC_{(0-24)}$ values will not exceed the maximum $AUC_{(0-24)}$ value observed at the NOAEL and for C_{max} the 95th percentile will not exceed the mean C_{max} and the NOAEL. The current predicted 5th -95th percentiles for $AUC_{(0-24)}$ and C_{max} values using repeat dose PK data from FTiH study and mean/individual $AUC_{(0-24)}$ and C_{max} values from the 13-week Monkey Study at 30 mg/kg/day (NOAEL) and 100 mg/kg/day are shown in Figure 2 and Figure 3, respectively.

Figure 2 Mean and 95% Prediction Interval for Human $AUC_{(0-24)}$ Values versus Mean and Individual Monkey C_{max} Values at Week 13

[figure not shown]
[figure not shown]

Figure 3 Mean and 95% Prediction Interval for Human Cmax values Versus Mean and Individual Monkey Cmax values at Week 13

6. STUDY POPULATION

Prospective approval of protocol deviations to recruitment and enrolment criteria, also known as protocol waivers or exemptions, is not permitted.

6.1. Inclusion Criteria

Participants are eligible to be included in the study only if all of the following criteria apply:

AGE
1. Participant must be 18 to 65 years of age inclusive, at the time of signing the informed consent.

TYPE OF PARTICIPANT AND DISEASE CHARACTERISTICS
2. Healthy as determined by the Investigator or medically qualified designee based on a medical evaluation including medical history, physical examination, neurological examination, laboratory tests and cardiac monitoring. A subject with a clinical abnormality or laboratory parameter(s) which is/are not specifically listed in the inclusion or exclusion criteria, outside the reference range for the population being studied may be included only if the Investigator in consultation with the Medical Monitor (if required) agree and document that the finding is unlikely to introduce additional risk factors and will not interfere with the study procedures. Note: Screened subjects with laboratory values outside of the normal range may be repeated once for inclusion into the study at the discretion of the Investigator.

WEIGHT
3. Body weight ≥ 50 kg and body mass index (BMI) within the range 19 - 30 kg/m ² (inclusive).

SEX
4. Male and/or Female Subjects a. Male participants: A male participant must agree to use contraception as detailed in Appendix 5 of this clinical study proposal during the treatment period and for at least 90 days after the last dose of study treatment and refrain from donating sperm during this period. b. Female participants: A female participant is eligible to participate if she is not pregnant (see Appendix 5), not breastfeeding, and at least one of the following conditions applies:

- | |
|---|
| 
i. Not a woman of childbearing potential (WOCBP) as defined in Appendix 5
OR
 
ii. A WOCBP who agrees to follow the contraceptive guidance in Appendix 5 during the treatment period and for at least 30 days corresponding to time needed to eliminate study treatment after the last dose of study treatment.
 |
|---|

INFORMED CONSENT

- | |
|---|
| 
5. Capable of giving signed informed consent as described in Appendix 3 which includes compliance with the requirements and restrictions listed in the ICF and in this protocol.
 |
|---|

6.2. Exclusion Criteria

Participants are excluded from the study if any of the following criteria apply:

MEDICAL CONDITIONS

- | |
|---|
| 
 History or presence of or current cardiovascular, respiratory, hepatic, renal, gastrointestinal, endocrine, hematological, or neurological disorders capable of significantly altering the absorption, metabolism, or elimination of drugs; constituting a risk when taking the study treatment; or interfering with the interpretation of data. History of herpes zoster (shingles) reactivation. Evidence of active or latent tuberculosis (TB) as documented by medical history and examination, chest x-rays (posterior anterior and lateral), and TB testing: either a positive tuberculin skin test (TST; defined as a skin induration <5 mm at 48 to 72 hours, regardless of Bacillus Calmette-Guerin (BCG) or other vaccination history) or a positive (not indeterminate) QuantiFERON-TB Gold test. |
|---|

NOTE: The choice to perform a TST or a QuantiFERON-TB Gold test will be made by the investigator according to local licensing and standard of care. The QuantiFERON-TB Gold test can only be used in countries where it is licensed, and the use of this test is dependent on previous treatment(s). This test may not be suitable if previous treatment(s) produced significant immunosuppression.

- | |
|---|
| 
 Alanine transaminase (ALT) >1.5x upper limit of normal (ULN). Bilirubin >1.5xULN (isolated bilirubin >1.5xULN is acceptable if bilirubin is fractionated and direct bilirubin <35%). Current or chronic history of liver disease, or known hepatic or biliary abnormalities (with the exception of Gilbert's syndrome or asymptomatic gallstones) QTc >450 msec |
|---|

NOTES:

- The QTc is the QT interval corrected for heart rate according to Bazett's

formula (QTcB), Fridericia's formula (QTcF), and/or another method, machine-read or manually over-read.

- The specific formula that will be used to determine eligibility and discontinuation for an individual subject should be determined prior to initiation of the study. In other words, several different formulae cannot be used to calculate the QTc for an individual subject and then the lowest QTc value used to include or discontinue the subject from the trial.
 - For purposes of data analysis, QTcB, QTcF, another QT correction formula, or a composite of available values of QTc will be used as specified in the Reporting and Analysis Plan (RAP).
8. History of serious or recurrent infections or has had an active infection within 14 days of receiving study medication.
 9. History of diagnosis of obstructive sleep apnoea or significant respiratory disorder. Childhood asthma that has fully resolved is permitted.
 10. Part A: History of active SIB within the past 6 months or any history of attempted suicide in a participant's lifetime.
 11. History of current evidence of febrile seizures, epilepsy, convulsions, significant head injury, or other significant neurologic conditions.

PRIOR/CONCOMITANT THERAPY

12. Past or intended use of over-the-counter or prescription medication, including herbal medications, within 7 days (or 14 days if the drug is a potential enzyme inducer) or 5 half-lives (whichever is the longest) prior to dosing. Specific medications listed in Section 7.6 may be allowed.
13. Subject received a vaccine (either live attenuated or now-live) within 30 days prior to randomisation, or plans to receive a live attenuated vaccine within 30 days + 5 half-lives (32 days) of the last dose of study medication.

PRIOR/CONCURRENT CLINICAL STUDY EXPERIENCE

14. Participation in the study would result in loss of blood or blood products in excess of 500 mL within a 56-day period.
15. Exposure to more than 4 new chemical entities within 12 months prior to the first dosing day.

DIAGNOSTIC ASSESSMENTS

16. Presence of Hepatitis B surface antigen (HBsAg) at screening Positive Hepatitis C antibody test result at screening.
17. Positive pre-study drug/alcohol screen.
18. Positive human immunodeficiency virus (HIV1 and 2) antibody test.
19. Regular use of known drugs of abuse.
20. Subjects with impaired renal function defined as Chronic Kidney Disease Epidemiology Collaboration (CKS-EPI) Creatinine > 1.6mg/dL with an age appropriate GFR ≤ 60 (mL/min/1.73 m²) estimated by the Chronic Kidney Disease Epidemiology Collaboration (CKD-EPI) equation [[Snyder](#), 2009 and [Levey](#), 2010].
21. An elevated C-reactive protein (CRP) outside of the normal reference range.

OTHER EXCLUSIONS

22. Regular alcohol consumption within 6 months prior to the study defined as:
 - For UK - an average weekly intake of >14 units for males and females. One unit is equivalent to 8 g of alcohol: a half-pint (~240 mL) of beer, 1 glass (125 mL) of wine or 1 (25 mL) measure of spirits.
23. Cotinine levels indicative of smoking or history or regular use of tobacco- or nicotine-containing products within 6 months prior to screening.
24. Sensitivity to any of the study treatments, or components thereof, or drug or other allergy that, in the opinion of the investigator or medical monitor, contraindicates participation in the study
25. Unwilling or unable to swallow multiple size 00 capsules as part of study participation.

PART B SPECIFIC CRITERIA

26. History of SIB as measured using the C-SSRS or a history of attempted suicide.
27. A positive anti-nuclear antibody (ANA) outside of the normal reference range.
28. Total cholesterol ≥ 300 mg/dL or triglycerides ≥ 250 mg/dL.

6.3. Lifestyle Restrictions**6.3.1. Meals and Dietary Restrictions**

- Refrain from consumption of red wine, Seville oranges, grapefruit or grapefruit juice, pomelos, exotic citrus fruits, grapefruit hybrids, or fruit juices from 7 days prior to each first dose of study treatment in Part A up until discharge from the unit. In Part B, subjects must refrain from consumption of red wine, Seville oranges, grapefruit or grapefruit juice, pomelos, exotic citrus fruits, grapefruit hybrids, or fruit juices from 7 days prior to the first dose of study treatment until after the final dose.

6.3.2. Caffeine, Alcohol, and Tobacco

- During each dosing period, participants will abstain from ingesting caffeine- or xanthine-containing products (e.g., coffee, tea, cola drinks, and chocolate) for 24 hours before the start of dosing until after collection of the final PK sample.
- During each dosing period, participants will abstain from alcohol for 24 hours before the start of dosing until after collection of the final PK sample.
- Use of tobacco products will not be allowed from 6 months prior to screening until after the final follow-up visit.

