PK Blood Sampling			X	X			
TID Dosing: PK samples to be taken pre-dose on Day 1 and then at the following time points post first-dose: 20min, 40min, 1hr, 1hr 30min, 2hr, 3hr, 5hr, 7hr, 7hr 20min, 7hr 40 min, 8hr, 8hr 30min, 9hr, 10hr, 12hr, 14hr, 14hr 20min, 14hr 40 min, 15hr, 15hr 30min, 16hr, 19hr, 22hr, 24hr.
 
BID Dosing: PK samples to be taken pre-dose on Day 1 and then at the following time points post first-dose: 20min, 40min, 1hr, 1hr 30min, 2hr, 3hr, 4hr, 6hr, 8hr, 10hr, 12hr, 12hr 20min, 12hr 40min, 13hr, 13hr 30min, 14hr, 15hr, 16hr, 19hr, 22hr, 24hr.

Neuro. Examination			←X→	X	←X→		
TID Dosing: Neurological examinations to be conducted either on Day -1 or pre-dose Day 1 and then at the subsequent time points post first-dose on Day 1: 2hr, 9hr, 16hr, 24hr and 48hr. Then 24 and 48hr after the last dose administered on Day 1.
 
BID Dosing: Neurological examinations to be conducted either on Day -1 or pre-dose Day 1 and then at the subsequent time points post first-dose: 2hr, 14hr, 24hr and 48hr. Then 24 and 48 hr after the last dose administered on Day 1.

Telemetry			←X→				Continuous at least 24hr post-evening dose. Initiate at least 15 min. prior to dosing.
12-Lead ECG	X	X	T	X	←X→		
Vital signs to include HR, BP, temperature and respiration rate.
 
TID Dosing: 12-Lead ECG and Vital Signs to be conducted on Day -1 and pre-dose on Day 1 and then at the subsequent time points post first-dose: 40min, 2hr, 4hr, 7hr (pre-2nd dose), 9hr, 14hr (pre-3rd dose), 16hr, 24hr and 48hr. Then 24 and 48hr after the last dose administered on Day 1.

Vital Signs	X	X	T	X	←X→	X	
BID Dosing: 12-Lead ECG and Vital Signs to be conducted on Day -1 and pre-dose on Day 1 and then at the subsequent time points post first-dose: 40 min, 2hr, 4hr, pre-2nd dose, 12hr 20 min, 14hr, 24hr and 48 hr. Then 24 and 48hr after the last dose administered on Day 1.
 
T = Triplicate.

Randomization		X					
Study Treatment			X ^b				
^b TID dosing: GSK2982772 or placebo will be administered using a 7hr, 7hr and 10hr dosing interval.
 
BID dosing: GSK2982772 or placebo will be administered using a 12hr dosing interval.

AE Review		←=====X=====→				X	
SAE Review		←=====X=====→				X	
Concomitant Medication Review	X	←=====X=====→				X	

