PK Blood Sampling			X	X				
TID Dosing: PK samples to be taken pre-dose on Day 1 and then at the following time points post first-dose: 20min, 40min, 1hr, 1hr 30min, 2hr, 3hr, 5hr, 7hr, 7hr 20min, 7hr 40 min, 8hr, 8hr 30min, 9hr, 10hr, 12hr, 14hr, 14hr 20min, 14hr 40 min, 15hr, 15hr 30min, 16hr, 17hr, 19hr, 22hr, 24hr.
 
BID Dosing: PK samples to be taken pre-dose on Day 1 and then at the following time points post first-dose: 20min, 40min, 1hr, 1hr 30min, 2hr, 3hr, 4hr, 6hr, 8hr, 10hr, 12hr, 12hr 20min, 12hr 40min, 13hr, 13hr 30min, 14hr, 15hr, 16hr, 19hr, 22hr, 24hr.
 
Remaining PK plasma samples from Part A may be analysed for metabolite sampling.

Neuro. Examination			←X→	X		←X→		
TID Dosing: Neurological examinations to be conducted either on Day -1 or pre-dose Day 1 and then at the subsequent time points post first-dose on Day 1: 2hr, 9hr, 16hr, 24hr and 48hr. Then 24 and 48hr after the last dose administered on Day 1.
 
BID Dosing: Neurological examinations to be conducted either on Day -1 or pre-dose Day 1 and then at the subsequent time points post first-dose: 2hr, 14hr, 24hr and 48hr. Then 24 and 48 hr after the last dose administered on Day 1.

Telemetry				←X→				Continuous at least 24hr post-evening dose. Initiate at least 15 min. prior to dosing.
12-Lead ECG	X	X	T	X		←X→		
Vital signs to include HR, BP, temperature and respiration rate.
 
TID Dosing: 12-Lead ECG and Vital Signs to be conducted on Day -1 and pre-dose on Day

Procedure	Screening (Up to 28 days before Day 1)	Study Period (Days)					Follow-Up (No more than 14 days post last dose)	Notes
		-1	1	2	3	4		
Vital Signs	X	X	T	X	←X→	X	
1 and then at the subsequent time points post first-dose: 40min, 2hr, 4hr, 7hr (pre-2nd dose), 9hr, 14hr (pre-3rd dose), 16hr, 24hr and 48hr. Then 24 and 48hr after the last dose administered on Day 1.
 
BID Dosing: 12-Lead ECG and Vital Signs to be conducted on Day -1 and pre-dose on Day 1 and then at the subsequent time points post first-dose: 40 min, 2hr, 4hr, pre-2nd dose, 12hr 20 min, 14hr, 24hr and 48 hr. Then 24 and 48hr after the last dose administered on Day 1.
 
T = Triplicate.
	
Randomization		X					Randomization can occur on either Day -1 or Day 1.	
Study Treatment			X ^b				
^b TID dosing: GSK2982772 or placebo will be administered using a 7hr, 7hr dosing interval.
 
BID dosing: GSK2982772 or placebo will be administered using a 12hr dosing interval.
	

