Procedure	Screening (Up to 28 days before Day 1)								Stu	dy Pe	riod (Days)								Follow- up (No more than 14 days post last dose)	Notes
		- 1	1	2	3	4	5	6	7	8	9	10	11	12	13	14	15	16	17		
																					Day 1 no later than 1hr prior to dosing. To be drawn pre- dose on Days 2, 4, 7 and 10.
Holter Monitoring (24- hour)	Х																				
Telemetry			>	()	<										>	<				Continuous at least 24 hr post-evening dose. Initiate at least 15 min. prior to dosing.
PK blood sampling			Xq	Xe	Xe	Xe	Xe		Xe		Xţ		Xţ			Xa					^d On Day 1, PK samples will be collected pre-dose and at the following time points post first-dose: 20min, 40min, 1hr, 1hr 30min, 2hr, 3hr, 5hr,

Procedure

Screening (Up to 28 days before Day 1)								Stu	dy Pe	riod (Days)								Follow- up (No more than 14 days post last dose)	Notes
	- 1	1	2	3	4	5	6	7	8	9	10	11	12	13	14	15	16	17		
																				7hr, 9hr and 11hr. • On Days 2,3 4, 5 and 7 pre- dose samples only. f Days 9, and 11: Cohort 2, 3 and Cohort 4 PK sampling will be collected pre- dose and at the following time points post first-dose: 20min, 40min, 1hr, 1hr 30min, 2hr, 3hr, 5hr, 7hr (prior to 2 nd dose) 7hr 20min, 7hr 40 min, 8hr, 8hr 30min, 9hr, 10hr, 12hr.

205184

Study Period (Days)		 		Follow- up (No more than 14 days post last dose)	Notes

Procedure	Screening (Up to 28 days before Day 1)		Study Period (Days)															more than 14 days post last dose)	Notes		
		- 1	1	2	3	4	5	6	7	8	9	10	11	12	13	14	15	16	17		
																					Cohort 5 is currently not planned to have PK assessment but may be included depending on outcome of food effect in Cohorts 2, 3 and 4. ^g Day 14 sampling for Cohorts 2, 3, 4 and 5 will be over 24hr according to the following schedules: For TID Dosing: PK samples to be taken pre-dose and then at the

Procedure	Screening (Up to 28 days before Day 1)		Study Period (Days)														Follow- up (No more than 14 days post last dose)	Notes			
		- 1	1	2	3	4	5	6	7	8	9	10	11	12	13	14	15	16	17		
																					following time points post first-dose: 20min, 40min, 1hr, 1hr 30min, 2hr, 3hr, 5hr, 7hr (pre-2 nd dose) 7hr 20min, 7hr 40 min, 8hr, 8hr 30min, 9hr, 10hr, 12hr, 14hr (pre 3 rd dose), 14hr 20min, 14hr 40 min, 15hr, 15hr 30min, 16hr, 17hr, 19hr, 22hr, 24hr. For BID Dosing: PK samples to be taken pre-dose on Day 1 and then at the

Procedure	ocedure Screening (Up to 28 days before Day 1)															Follow- up (No more than 14 days post last dose)	Notes				

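### The caffeine and alcohol restriction ends at the last PK sample, 12 to 38 h before in-house telemetry, ECG and vital-sign monitoring ends, so late safety readings may include permitted intake

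*Protocol*

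**What the plan says.** Protocol 6.3.2 applies the caffeine/xanthine and alcohol restriction in each dosing period "for 24 hours before the start of dosing until after collection of the final PK sample". Amendment 02 keeps this text.

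The final PK sample is the 24 h sample in both regimens. The Part A schedule (Protocol 2.1) ends "15hr 30min, 16hr, 17hr, 19hr, 22hr, 24hr" for TID and "13hr 30min, 14hr, 15hr, 16hr, 19hr, 22hr, 24hr" for BID. For Part B, the schedule reproduced in SAP 10.2.1.2 states: "Day 14 sampling for Cohorts 2, 3, 4 and 5 will be over 24hr".

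Safety monitoring is tied to the last dose instead. Telemetry is "Continuous at least 24hr post-evening dose". For ECG and vital signs, Protocol 2.1 lists TID times ending "14hr (pre-3rd dose), 16hr, 24hr and 48hr" and adds: "Then 24 and 48hr after the last dose administered on Day 1". SAP 10.2.1.2 places Part B sets 24 and 48 h after both the first and the last dose on Day 14. Participants stay in the unit to Day 4 of each Part A period and to Day 17 in Part B.

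In Part A, the neighbouring rule on citrus, fruit juice and red wine (Protocol 6.3.1) runs "up until discharge from the unit". In Part B that rule ends after the final dose.

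**The concern.** Vital signs and 12-lead ECG are primary endpoints, and the SAP summarises them as change from baseline. SAP 5.2 takes the latest pre-dose value as baseline, normally Day 1 pre-dose, after 24 h without caffeine or alcohol. Sets taken after the restriction ends do not have that protection, although the participants are still in the unit.

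Small shifts are enough to be flagged: SAP 10.8.3 starts flagging heart-rate change at 15 bpm. The Dose Escalation Committee reviews flagged vital signs and telemetry. In Part B its data set includes telemetry and ECG findings through Day 16 (Protocol 10.5), whereas the restriction ends on Day 15. Amendment 02 was prompted by cardiac arrhythmias, so an avoidable influence on late rhythm findings deserves attention. With 3 or 5 placebo participants per cohort, an isolated late finding is hard to interpret. No record of caffeine intake is scheduled against which it could be checked.

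**Working it through.** All times are hours after the first dose of the day: Day 1 in Part A, Day 14 in Part B.

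**Inputs**
- Restriction ends: 24 h (Protocol 6.3.2 with the PK rows of Protocol 2.1 and SAP 10.2.1.2).
- Last dose: TID 7 + 7 = 14 h, which reproduces the 14 h pre-third-dose time in Protocol 2.1; BID 12 h.
- Telemetry ends: last dose + 24 h, as a minimum.
- Last timed in-house ECG and vital signs: last dose + 48 h.

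**Time after the restriction ends**

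| | TID | BID |
|---|---|---|
| Telemetry ends | 14 + 24 = 38 h | 12 + 24 = 36 h |
| Telemetry after restriction | 38 − 24 = 14 h | 36 − 24 = 12 h |
| Last timed ECG/vital signs | 14 + 48 = 62 h | 12 + 48 = 60 h |
| Gap after restriction | 62 − 24 = 38 h | 60 − 24 = 36 h |

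**Part A post-dose ECG/vital-sign sets**
- TID: 0.67, 2, 4, 7, 9, 14, 16, 24, 38, 48 and 62 h. Three of 11 (38, 48, 62) fall after the restriction.
- BID: 0.67, 2, 4, 12, 12.33, 14, 24, 36, 48 and 60 h. Three of 10 (36, 48, 60) fall after it.

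The 24 h set counts as inside, because Protocol Section 2 puts ECG and vital signs before blood draws at the same nominal time.

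**Part B.** Taking the dosing period as the whole 14-day course, the final PK sample is on Day 15. Telemetry and ECG around Day 1 are therefore fully covered. The gaps in the table arise only after the Day 14 doses. The Part B grid also marks vital signs on Day 17 without a clock time; these are not counted.

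**How much drug is present.** Protocol 5.7 gives a half-life of about 2 to 3 h. The restriction ends 24 − 14 = 10 h (TID) or 24 − 12 = 12 h (BID) after the last dose. Simple first-order decay from the time of dosing, ignoring absorption, leaves:
- TID: 2^(−10/2) = 3% to 2^(−10/3) = 10%.
- BID: 2^(−12/2) = 2% to 2^(−12/3) = 6%.

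The unrestricted readings are therefore washout readings at low concentration.

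**Treatment-emergent window.** SAP 10.4.2 closes at the treatment stop date + 1 day, which is Day 2 in Part A. With morning dosing, the 36/38 h set falls on Day 2, inside or at the edge of the window. The 48 h and 60/62 h sets fall on Day 3, outside it.

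**The case against.** The strongest answer is that lifting a prohibition does not show intake. Participants are confined, Part A meals are standardised, and no passage says that caffeine or alcohol is served after 24 h. Part A also bars red wine until discharge under 6.3.1. All dose peaks and most of the exposure lie inside the restriction, placebo participants follow the same rule, and Amendment 02 addressed rhythm by adding a screening Holter and raising placebo from 3 to 5 per cohort.

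Most of this stands, and it limits the point. A reader might infer that the late readings are not comparable with baseline; the documents support only that they may not be. A reader might also infer that the last third of telemetry (14/38 = 37% TID, 12/36 = 33% BID) loses a caffeine-free baseline. It has none to lose: Part A guarantees about 15 minutes of pre-dose telemetry, the Part B rhythm baseline is a screening Holter outside the 24 h restriction, and the SAP lists no telemetry display. Nor do late heart-rate changes automatically count as treatment-emergent. That flag applies to adverse events by onset, and a measured value becomes an adverse event only if the investigator judges it clinically significant.

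Confinement does not close the gap. The meal text does not mention caffeine, and Part B meals on Days 16 and 17 follow the site's own schedule. Nor is 6.3.1 a uniform precedent, because in Part B its rule stops earlier than the caffeine rule.

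**Conclusion.** The timing gap is real and present in the current text. After the restriction ends there remain at least 12 h (BID) or 14 h (TID) of telemetry, and timed ECG and vital-sign sets up to 36 h (BID) or 38 h (TID) later. In Part B this applies only after Day 14. The late ECG and vital-sign sets may include permitted intake that the Day 1 baseline excludes, and late telemetry is recorded without control of intake.

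The consequence is possible noise and individual misattribution in low-concentration washout readings. A reader might infer bias between active and placebo, but the rule is the same for both and the documents give no ground for a systematic difference. The conclusion assumes that the unit does not already withhold caffeine and alcohol until discharge, on which the documents are silent, and that the schedule is kept at nominal times. It is a cheap improvement to a design choice, not a contradiction in the plan.

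**What to change.** In Protocol 6.3.2, end the caffeine and alcohol restriction at discharge from the unit: Day 4 of each Part A period and Day 17 in Part B. It then covers the last in-house telemetry, ECG and vital signs. If the unit already serves neither, a sentence saying so would do the same job. The cost is one phrase and about two more caffeine-free in-house days per period, with no new procedure and no change to the SAP.
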